**[name]**  
**[contact]**  
**[contact]**

**[name].**  
**University of Utah**  
**Division of Infectious Disease**  
**[name]**  
**[name]**  
**[contact]**

**BACKGROUND AND INTRODUCTION:** Up to one-third of patients with irritable bowel syndrome (IBS) describe the onset of their symptoms following an episode of acute gastroenteritis. This is called post-infective IBS (PIIBS). It is associated with an increase in inflammatory mediators such as prostaglandins, cytokines, and nerve growth factors. Routine colon histology is usually normal; however, there is often an increase in the number of mast cells and T-cells on microscopic examination. It is thought that the initial inflammatory response triggers a cascade of events (mediated by incorporation of Toll-like receptors and NF- $\kappa$ B) leading to proliferation of mast cells and activation of enterochromaffin (EC) cells. Intestinal mucosal mast cells attract inflammatory cells and initiate the innate and adaptive immune system manifested by invasion of T-lymphocytes, and also enhance visceral hypersensitivity and abdominal pain. Enterochromaffin cells secrete serotonin which regulates intestinal motility and secretion. It remains unclear whether the inflammation is the response to injury or initiates the disease. Nor is it known why the disease becomes self-perpetuating.

NF- $\kappa$ B (nuclear factor kappa-light chain-enhancer of activated B cells) is a transcription factor that plays a central role in inflammation and immune regulation. Mesalamine (5-ASA) is a PPAR  $\gamma$  (peroxisome proliferator-activated receptor  $\gamma$ ) agonist which among other things inhibits NF- $\kappa$ B. There is anecdotal evidence that it is effective in the treatment of microscopic colitis which has many pathophysiologic similarities to PI-IBS. We hypothesize that patients with PI-IBS are also likely to respond to mesalamine.

A recent study in IBS patients demonstrated a reduction in colonic mast cells after mesalamine but no improvement in symptoms. A double-blind placebo controlled study of mesalamine by our group also failed to show improvement in symptoms but did demonstrate a trend toward improvement in quality-of-life (QOL) suggesting that other mechanisms may be involved- perhaps suppression of the immune response which is partly responsible for the extraintestinal symptoms of fatigue, etc. Compliance was a problem in this study as patients were not receptive to taking 4 tablets of mesalamine twice per day. We propose that compliance and therapeutic response could be improved by using long acting mesalamine. Salt Lake City is an ideal area to conduct this study in that there is a large population of Mormon missionaries and who return from abroad with altered bowel function. We have previously demonstrated that most of these patients have PI-IBS.

The purpose of this study is to evaluate the effects of long acting mesalamine (Lialda®) in patients with PI-IBS. We will evaluate gastrointestinal symptoms, IBS specific quality of life (IBS-QOL) before and after treatment with Lialda®.

#### **Significance of this study:**

This study will test long acting mesalamine in the management of PI-IBS. It has the potential to improve QOL and perhaps gastrointestinal symptoms, in patients with PI-IBS. The results of this study, if positive, will provide preliminary data for a large scale clinical trial.

#### **Aim:**

To determine if mesalamine will relieve symptoms, improve QOL and reduce inflammation in patients with PI-IBS.

#### **IBS**

IBS is characterized by abdominal pain or discomfort associated with altered bowel function (diarrhea and/or constipation) in the absence of any structural abnormality. It is a poorly understood disorder that is probably a heterogeneous group of conditions producing similar symptoms. IBS is associated with reduced QOL and significant economic burden. It is the most frequent GI disorder seen by physicians, comprising 50% of referrals to gastroenterologists and as many as 3.5 million visits to physicians each

year in the United States. The direct cost of IBS in the US is estimated at \$1.5 to 10 billion and the indirect cost, \$20 billion. The cause of IBS is not known. The speculated mechanisms of IBS include altered GI motility, visceral hypersensitivity, aberrant brain-gut interaction, and psychological factors, perhaps with a genetic predisposition. A proposed triggering mechanism in patients with PI-IBS is mucosal injury with subsequent inflammatory/ immune response which becomes self-perpetuating.

### PI-IBS

IBS occurs in 7% to 30% of subjects after an episode of gastroenteritis. Several factors have been shown to predispose to PI-IBS: severity of the initial illness, bacterial toxigenicity, hypochondriasis, depression and adverse life events in the previous 3 months. PI-IBS is characterized by predominance of diarrheal symptoms, less psychiatric illness, and increased serotonin-containing enterochromaffin cells compared to those with non-PI-IBS.

There are several factors which suggest that inflammation plays a part in the pathogenesis of PI-IBS. For example, an infection activates mast cells in the GI tract. When activated, mast cells release humoral mediators which induce the adaptive and subsequently the innate immune response leading to attraction of both cytotoxic and helper T- lymphocytes. Mast cell derived cytokines TNF- $\alpha$  and IL-1 $\beta$  also play an important role in generation of visceral hypersensitivity and abdominal pain. Activated enterochromaffin cells secrete serotonin which regulates intestinal motility and secretion. Anxiety and depression which are more common in IBS are also related to serotonin and can cause bowel symptoms compatible with IBS.

Recent studies have demonstrated that acute gastroenteritis triggers a self-perpetuating immune and chemical response which is responsible for maintaining symptoms after the acute injury has resolved. In PI-IBS, the colon is grossly normal but biopsy reveals an increased number of EC and mast cells as well as sub-epithelial inflammatory cells, specifically T-lymphocytes. Chadwick et al demonstrated an increased number of activated T lymphocytes in all 77 symptomatic patients with IBS. Patients with PI-IBS show an increased level of expression of the pro-inflammatory cytokine IL-1 $\beta$  in the rectal mucosa. Other studies have shown high levels of the proinflammatory cytokines IL-1 $\beta$ , IL-6 and TNF- $\alpha$  in peripheral blood mononuclear cells. It has also been speculated that IBS patients may be more susceptible to infection and are thus genetically predisposed to produce lower amounts of the anti-inflammatory cytokine, IL-10. A recent study has shown abnormalities in the IL-10/IL-12 ratio in patients with IBS favoring inflammation. Mast cell degranulation and increased pro-inflammatory cytokines may contribute to symptom perception as they have been shown to generate visceral hypersensitivity via direct activation of sensory nerves.

Enterochromaffin cells contain 85 percent of the total body serotonin which is involved in visceral hypersensitivity, the peristaltic reflex and intestinal secretions. However, inflammation alone is not sufficient to cause IBS as most of the patients with gastroenteritis recover completely. Psychologic stress is also known to affect gut function. It has been shown to release mast cell and enterochromaffin cell mediators in the colon and thus may play a role in the perpetuation of IBS.

### Mesalamine

5-aminosalicylic acid (5-ASA) is a topically acting anti-inflammatory agent that is used in the treatment of inflammatory bowel disease. 5-ASA activates the peroxisome proliferator-activated receptor  $\gamma$  (PPAR- $\gamma$ ). PPAR- $\gamma$  is a transcription factor which is highly expressed in the colonic epithelium. It modulates cytokine production and, specifically, decreases activity of NF- $\kappa$ B, which is a central factor in inflammation. It also reduces synthesis of prostaglandins and leukotrienes which are also mediators of the inflammatory response.

### Mesalamine and PI-IBS

There is strong evidence that PI-IBS is triggered by inflammation and persists because of self-perpetuating immune response: 1) it starts after gastroenteritis, 2) presence of mast cells which induce the innate and adaptive immune systems 3) the increase in pro-inflammatory and decrease in anti-inflammatory cytokines in blood, 4) PI-IBS shares many of the features of lymphocytic colitis (chronic diarrhea, grossly normal endoscopic findings, mucosal inflammation and a benign course).

It is logical that an anti-inflammatory agent will be effective in PI-IBS. Experimental data show that inflammation, even if mild, can lead to persistent changes in gastrointestinal nerve and smooth muscle function, resulting in dysmotility, rectal hypersensitivity and gastrointestinal dysfunction. Research has also shown that functional changes in mice intestine after infection may be reversed using non-selective or selective anti-inflammatory agents administered after recovery from infection Dunlop et al studied the role of oral steroids in reducing inflammation and enterochromaffin cells numbers. Their study demonstrated a significant decrease in the T-lymphocyte number in the lamina propria but was not associated with an improvement in symptoms. A recent study evaluated mesalamine in non-selective patients with IBS. There was improvement in colon histology but no improvement in symptoms. We have shown that there is trend to improvement in QOL with mesalamine.

The purpose of this study is to evaluate the effects of long acting mesalamine (Lialda®) in patients with PI-IBS. We will evaluate gastrointestinal symptoms and IBS specific quality of life (IBS-QOL) before and after treatment with Lialda®

### **OBJECTIVES:**

**Objective #1:** Determine the efficacy of mesalamine in patients with PI-IBS.

Hypothesis: Treatment with mesalamine compared to placebo will improve QOL, and global as well as individual symptoms of IBS

### **PARTICIPANT SELECTION CRITERIA:**

#### Patient Population

Ambulatory patients, 18 years of age or older with PI-IBS symptoms for at least 6 months, will be enrolled in the study. The study population will consist of previously healthy patients who developed IBS after an episode of gastroenteritis. Patients will be identified by the Bowel Disease Questionnaire which is sensitive to Rome Criteria. Rome III criteria will be used to define IBS. PI-IBS patients are usually diarrhea-predominant and patients whose predominant symptom is constipation will not be enrolled in this study. Patients will be recruited from the Internal Medicine and Gastroenterology clinics at the University Hospital and the VA Medical Center.

#### Inclusion Criteria

1. Men and women age 18-75 years
2. Rome III criteria for IBS
3. Symptom onset after apparent acute gastroenteritis
4. Symptoms of 6 months or greater duration
5. Normal gross appearance of the colonic mucosa other than erythema and polyps
6. Negative markers for celiac disease (tissue transglutaminase antibody or endomysial antibody).
7. No clinically significant abnormality in thyroid function (Thyroid Stimulating Hormone) and serum calcium
8. Stable medication regimens for more than 1 month.

9. Sexually active female patient of child bearing potential have negative urine pregnancy test or practices accepted method of birth control during the study.
- 10.

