#### Exclusion Criteria

1. Age <18 or > 75 years
2. Constipation-predominant IBS.
3. Clinically significant chronic cardiac, pulmonary, hepatic, renal dysfunction or HIV
4. Presence of active malignancy Current evidence of any gastrointestinal disorder such as celiac disease, inflammatory bowel disease, chronic pancreatitis, scleroderma, HIV, small bowel or colonic resection, paraplegia or quadriplegia
5. Current evidence of drug or alcohol abuse as judged by the investigator
6. Allergy to mesalamine or aspirin
7. Investigator perception of patient's inability to comply with the study protocol
8. Unstable psychiatric disease
9. Recent change in gastrointestinal medications

**DESIGN:** Randomized double-blind placebo-controlled.

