### **STUDY PROCEDURES:**

This study will be conducted at the University of Utah and the VA Medical Center. Information collected at the VA will be stored at the VA. For purposes of statistical analysis the information from the VA will be de-identified and sent to the University of Utah.

All patients will have a complete blood count, comprehensive biochemical profile (including serum calcium), thyroid-stimulating hormone (TSH), tissue transglutaminase antibody (TTG), C- reactive protein, and stool examination for electrolytes (optional), ova and parasite, C.difficile toxin (not required if stool is formed), Calprotectin or lactoferrin, and Giardia antigen. These tests will not be repeated if they were collected in the last 6 months. Blood and stool samples will be collected for storage if the patient consents. Flexible sigmoidoscopy and biopsy of the colonic mucosa will be performed in all patients at the beginning of treatment. Patients with red flag symptoms (onset in older than >50 years, progressive or non-fluctuating symptoms, unexplained weight loss, rectal bleeding or anemia, family history of colon cancer, fever, abnormal examination or laboratory tests) will have colonoscopy and biopsy. Patients with structural, biochemical, or infective disorders will be excluded from the study. A flexible sigmoidoscopy or colonoscopy will not be done if an acceptable biopsy was completed within 5 years. If the procedures are done a biopsy will be collected for storage.

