#### *Treatment Schedule*

This study will compare mesalamine two (Lialda®) 1.2 gm tablets orally daily to placebo in 68 patients with diarrhea predominant PI-IBS. The patients will be consented and enter into the screening which can last up to 8 weeks. This will be followed by an 8 week treatment period.

Patients will be re-consented to the newest version of the consent form if changes have been made while they are enrolled on the study. The patient may not be rescreened if there is no change in patient's symptoms if they are outside the screening window.

All patients will fill out the following questionnaires:

- 1) The Bowel Symptom Scale (BSS) at the beginning, at 4 weeks and at the end of the study period to assess any change based simply on admission to the trial.
- 2) The BSI-18 at the beginning of the screening period.
- 3) The IBS-QOL at the beginning, at 4 weeks and end of treatment.
- 4) The Nepean Dyspepsia Index at the beginning, 4 weeks and end of treatment as well as during the mail-in/phone call visits. BDQ (Bowel Disease Questionnaire) at screening.

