#### Time Line

##### *Location of Study*

This study will be performed at the University of Utah Hospital and Clinics and the VA Medical Center.

*Time Table of study:* Approximately 1 Years from the start of patient recruitment

Subject recruitment will start immediately upon IRB approval and continue throughout the duration of the study. We estimate that 50% of recruited patients will qualify for enrollment. Sixty-eight patients with diarrhea-predominant or mixed IBS (with diarrhea as predominant symptom) will be enrolled at the rate of 1-2 per week. The estimated dropout rate is 10%, leaving 64 patients to study. This population will include but not be limited to returned missionaries. We have previously worked with missionaries who have high prevalence of PI-IBS.

*Study visits* (Table 1. Figure 1.)

First visit:

Orientation to the study and informed Consent

Inclusion/Exclusion check

History and physical examination,

Questionnaires: BDQ, IBS-QOL, BSI-18, BSS, Nepean Dyspepsia Index (NDI)

Blood and stool tests (not repeated if done in past 6 months unless there has been an alteration in the symptoms)

Collection of stool sample for storage (if consent is given)

Urine pregnancy Test for women of child bearing potential

Instructions to complete 2 week stool diary during 8-week run in period

Second visit:

Flexible sigmoidoscopy/ colonoscopy with biopsy, if indicated (not repeated if performed during last 5 years, results within normal limits and no change in symptoms)

Third visit

Subjects will be randomly assigned to either two Lialda 1.2gm tablets daily or two placebo tablets daily according to a block randomization schedule generated by the statistician. Medicines will be provided by and dispensed at the Pharmacy. Medication may be mailed at patients' convenience and they will be informed on dosing and storage of medication by telephone.

Mail-in/ telephone visit

Patients will be asked to fill BSS IBS-QOL and NDI at week 4 of the 8 week treatment either by mail or on telephone.

Fourth visit

End of treatment- Questionnaires-BSS, IBS-QOL, and NDI and physical examination

Study drug count

Return all unused study drug and the study drug bottle(s)

**Standard of Care vs. Research-Related Procedures:** all procedures for this study are research-related.

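### Inclusion item 9 joins the negative pregnancy test and birth control with 'or', so as worded a positive first-visit test does not bar a woman who practises contraception

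*Combined protocol and SAP*

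**What the plan says.** In the combined protocol and SAP, item 9 of the Inclusion Criteria applies to sexually active women who could become pregnant. It requires that they "have negative urine pregnancy test or practices accepted method of birth control during the study".

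Four other places bear on it.

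- **Exclusion Criteria.** There are nine items, and none mentions pregnancy or a positive test. The only one specific to the study drug is item 6, "Allergy to mesalamine or aspirin". The nearest discretionary one is item 7, "Investigator perception of patient's inability to comply with the study protocol".
- **Study Procedures.** A separate sentence adds: "Patients with structural, biochemical, or infective disorders will be excluded from the study".
- **Time Line, Study visits, first visit.** The list includes "Urine pregnancy Test for women of child bearing potential" and, among the same tasks, "Inclusion/Exclusion check". It gives no action for a positive result.
- **Study Procedures table.** There is no row for a pregnancy test.

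**The concern.** An eligibility rule on pregnancy, backed by a scheduled test, is evidently there to keep pregnant women out of the trial. Item 9 instead offers two alternative ways to qualify, and the second does not depend on the test result. Staff who follow the text exactly would record a positive test, note that the woman uses contraception, and find item 9 met. She could then be randomized to 8 weeks of mesalamine or placebo.

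What is at stake is eligibility and participant safety, not inference. The trial runs at two institutions, and study medication may be mailed at the third visit, where no repeat test is listed. The written criterion and the first-visit check are therefore the only pregnancy safeguards visible in the plan. The documents give no figure for the risk of mesalamine in pregnancy, and none is assumed here.

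**Working it through.** No arithmetic applies and the plan states no figure to reproduce. The check is to apply item 9 to each combination of test result and contraception, then look for other text that would bar the doubtful case.

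**Step 1. Item 9 as written (either condition is enough).**

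| Urine test | Contraception practised | Item 9 met? |
|---|---|---|
| Negative | Yes | Yes |
| Negative | No | Yes |
| Positive | Yes | **Yes** |
| Positive | No | No |

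The third row is the fault. The table only spells out what 'or' means. The four rows are not equally likely, so counting them says nothing about how many patients are affected.

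**Step 2. Does any other visible text bar the third row?**

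- The nine exclusions: no. Item 6 is about allergy. Item 7 is about ability to comply, which a positive test does not in itself put in doubt.
- The exclusion sentence under Study Procedures: no. It names three kinds of disorder, and pregnancy is none of them.
- The first-visit list: it obtains the result but attaches no consequence to it.
- The Study Procedures table: no pregnancy-test row, so no rule.

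**Step 3. Does a kinder reading of 'or' remove the problem?** Item 9 could mean that only women not using contraception need a test. The first-visit list does not fit that reading, because it schedules the test for all women of child-bearing potential, with no exception for contraceptive users. Their results would be known, and item 9 would still give a positive one no effect.

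**Step 4. Compare possible repairs.**

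| Rule | Positive test admitted? | Negative test, no contraception admitted? |
|---|---|---|
| 'Or' (as written) | Yes, with contraception | Yes |
| Negative test required on its own | No | Yes |
| 'And' | No | No |

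Requiring the negative test on its own removes the faulty case and loses no woman with a negative test who qualifies now. Changing 'or' to 'and' would also turn away women with a negative test who do not use contraception.

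**The case against.** The strongest reply is that the case hardly exists. It needs a woman who tests positive, is still counted as practising birth control, and is then randomized by an investigator who has seen the result. In ordinary usage a woman known to be pregnant is not meeting a birth-control criterion, and the test sits in the same visit list as the eligibility check. As a statement about frequency, this stands. It does not rescue the wording: item 9 is satisfied by practising a method, not by the method having worked.

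A second reply is that absence can be asserted only of what can be read. Inclusion item 10 is a bare number in the available text, and some pages, consent material among them, are not in the public copy. This also stands, and it limits the claim to the visible text. If a bar on pregnancy did appear elsewhere, item 9 would conflict with it and would still need correcting.

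A third reply is that making the test stand alone could discard item 9's mention of contraception, the only visible text about pregnancy risk after the first visit. That is right, and the fix below keeps it.

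A fourth is that pregnancy starting after the first visit is the likelier route to exposure. The plan says "The patients will be consented and enter into the screening which can last up to 8 weeks", and 8 weeks of treatment follow, so up to 8 + 8 = 16 weeks can separate the only listed test from the end of treatment. This is a fair observation about a separate question, the age of the test result, which correcting the connective does not answer.

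**Conclusion.** The point holds as a wording error in a safety criterion. Read literally, item 9 lets contraception stand in for a negative test, and no visible exclusion or stated action on a positive result corrects this. The size is small: probably very few, if any, of the 68 patients. The documents give no count. Sample size, endpoint and analysis are unaffected. It is worth correcting because the rule gives the wrong answer when followed, and because correction costs almost nothing.

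The conclusion assumes that the scheduled test was meant to decide eligibility, which its place beside the eligibility check supports, and that the missing pages and blank item 10 contain nothing that changes the reading.

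Three stronger readings are not supported.

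- A reader might infer that the trial intends or expects to enrol pregnant women. The scheduled test points the other way.
- A reader might infer that the plan contains no bar on pregnancy anywhere. Only the visible text can be judged.
- A reader might infer that 'or' was a slip for 'and', so that contraception is compulsory. The documents do not settle whether the drafters wanted both conditions.

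**What to change.** 1. Add one line to the Exclusion Criteria: *Positive urine pregnancy test.*
2. Reword item 9: *Every woman of child-bearing potential must have a negative urine pregnancy test at the first visit; use of birth control does not replace the test.* This also matches the criterion to the group already tested at that visit, which is wider than the sexually active women named in item 9 now.
3. Keep contraception as its own statement: *Sexually active women of child-bearing potential: accepted contraceptive method throughout the study.* The sponsor should say whether this is mandatory. If it is, women with a negative test who do not use contraception will no longer qualify. If it is advice only, no woman with a negative test who qualifies now is lost.

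The cost is one added exclusion line and one reworded item. The test is already scheduled at the first visit, so no new procedure is needed.
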